## **6.6. Appendix 6 Medical History**

Medical history by System Organ Class (SOC) and Preferred Term (PT) will be summarized on the SS. A separate table will be created for Medical history ongoing at baseline (“Is the medical history disease/condition or event still ongoing?” = ‘Yes’ in the ‘General Medical History eCRF’ form). All Medical history will also be listed.

## **6.7. Appendix 7 Intervention Compliance**

Compliance through EOT will be summarized descriptively, including in the summary the following compliance categorization: < 80%, 80–120% and > 120%.

Compliance will be calculated as follows, for each strength dispensed:

Compliance = [(number of tablets dispensed - number of tablets returned)/2 x total duration of treatment period] x 100.

Compliance will be calculated only if the answer to the question “Was drug accountability performed for returned study treatment?” is ‘Yes’.

Compliance will also be listed.

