6.2.1. Study Intervention Up-Titration

Based on the GRIPHON study, the effect of selexipag on the composite endpoint of death from any cause or a complication related to PAH is consistent across different IMDs. The goal of the up-titration is to permit each participant to reach his/her personal highest tolerated dose without unmanageable prostacyclin-associated adverse effects.

Study intervention will be up-titrated to allow each participant to reach their IMD, in the range of 200 to 1,600 µg twice daily.

The study intervention will be up-titrated from Day 1 to the end of Week 12 (Day 84). Dosing will start at 200 µg twice daily. The site will call the participant once a week from the end of Week 1 to the end of Week 12 and decide whether to increase the dose by 200 µg twice daily ([Table 2](#)) if possible. Up-titration will be flexible and may be adapted in case of adverse effects that cannot be relieved with symptomatic treatment^e. In this case, the site may either postpone up-titration by 1 week or down-titrate study intervention.

^e Such as headache, diarrhea, nausea and vomiting, jaw pain, myalgia, pain in extremity, arthralgia, and flushing.

The dose reached at the end of Week 12 will be considered the participant's IMD and will be maintained until EOT.

Table 2: Up-Titration Guide

Weeks	Days	Target selexipag dose (µg, twice per day) ^a	Comments
1	1-7	200	In case of adverse effects that cannot be relieved with symptomatic treatment, postponement of up-titration by 1 week or down-titration should be considered.
2	8-14	400	
3	15-21	600	
4	22-28	800	
5	29-35	1000	
6	36-42	1200	
7	43-49	1400	
8	50-56	1600	
9-12	57-84	Buffer period to permit up/down-titration to ensure IMD is reached at the end of Week 12.	
13-52	85-364	IMD	

IMD individual maintenance dose

^a On Day 1, the participant will receive only 1 dose, and at each dose change the first intake of the new dose should be taken in the evening.

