6.5. Study Intervention Compliance

Study intervention compliance will be based on study intervention accountability. Study intervention compliance will be calculated by site personnel at each site visit using the below formula and entered in the eCRF:

For each strength dispensed:

Compliance $[(\text{number of tablets dispensed} - \text{number of tablets returned}) / \text{total number of tablets that should have been taken during the period}^{\text{f}}] \times 100$.

Between visits, compliance is expected to be between 80% and 120%. Compliance values outside of this range will be considered as a protocol deviation, which will be reported in the clinical trial management system by the clinical research associate. During the course of the study, the investigator or designated study-site personnel will be responsible for providing additional instruction to reeducate any participant who is not compliant with taking the study intervention. This discussion and its outcome must be documented in the source documents.

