6.7. Study Intervention Dose Modification

Any dose/dosage adjustment should be overseen by medically-qualified study-site personnel (principal or sub-investigator), unless an immediate safety risk appears to be present. See Section 6.2.1 for titration of study intervention during the first 12 weeks of treatment.

For participants with moderate hepatic impairment (Child-Pugh Class B) or using moderate inhibitors of CYP2C8 (eg, clopidogrel, deferasirox, teriflunomide, leflunomide) concomitantly with the study intervention, dosing frequency of study intervention must be reduced to once a day. Dosing

^f According to the study intervention administration log

frequency of selexipag should be reverted to twice daily when co-administration of moderate CYP2C8 inhibitor is stopped¹⁶.

It has been shown that, when moderate or strong inducers of CYP2C8 are used in combination with selexipag, the exposure to selexipag active metabolite is reduced by half. Dose adjustment of selexipag may be required with concomitant administration of inducers of CYP2C8 (eg, rifampicin, carbamazepine, phenytoin).

The effect of strong inhibitors of UDP-glucuronosyltransferase (UGT)1A3 and UGT2B7 (eg, valproic acid, probenecid, and fluconazole) on the exposure to selexipag or its active metabolite has not been studied. Concomitant administration may result in an increase in exposure to the active metabolite. Therefore, caution is required when these medicinal products are administered concomitantly with selexipag.

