## 1.2. Study Design

This is an open-label, multicenter, single-arm, interventional study to assess the effect of selexipag in adult participants ( $\geq 18$  to  $< 65$  years) with a diagnosis of PAH up to 52 weeks on study intervention.

The duration of individual participation will be approximately 60 weeks. The study will be conducted in 3 phases: a 28-day screening phase, a 52-week intervention phase (which will include an initial 12-week up-titration period), and a post-intervention safety follow-up period of at least 30 days. Primary and secondary objectives will be evaluated up to Week 26 and exploratory objectives will be evaluated up to Week 52.

The study comprises the following periods:

- **Screening period:** Informed consent signature marks both the start of the study and the start of the screening period.

This period serves to assess eligibility (medical history, treatments, blood tests) and to perform baseline efficacy assessments (MRI, Echo, 6MWD, WHO FC, NT-proBNP, and exploratory blood tests). Screening may last up to 28 days. A participant who is temporarily ineligible may be re-screened. Note: in case MRI, Echo, 6MWT or WHO FC assessment was made as part of routine practice in a way that fully complies with the study requirements, and within 28 days before Day 1, these data can be used for the study.

- **Treatment period:** Starts with the first dose of study drug (Day 1 of study) and ends with EOT on the day of the last dose of the study drug which is at Week  $52 \pm 7$  days or at premature discontinuation of study intervention. This period includes:
  - **Day 1:** Day 1 is defined as the day when a participant receives the first dose of study intervention. First dosing should occur at the site. Day 1 may occur once screening assessments are completed, and no later than 28 days after informed consent signature. For re-screened participants, all screening assessments must have been made (or repeated) within 28 days before Day 1.
  - **Up-titration:** During this period, study intervention will be up-titrated from Day 1 to the end of Week 12 (Day 84). Weekly phone calls from the site to participant will be performed to guide the up-titration and collect safety information. At the end of Week 4 (+ 7 days) and Week 12 (+ 7 days) and participants will return to the site for a return/dispensing visit; no assessments will be performed at these site visits.

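### SAP 6.7 calculates compliance per strength but divides by twice the whole treatment period, so a fully adherent one-week strength scores 1.8–1.9% at 364 days where Protocol 6.5 gives 100%

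*SAP*

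**What the plan says.** SAP 6.7 states the level of calculation: "Compliance will be calculated as follows, for each strength dispensed". The formula is "Compliance = [(number of tablets dispensed - number of tablets returned)/2 x total duration of treatment period] x 100". The scope is "Compliance through EOT will be summarized descriptively", with results sorted into below 80%, 80–120% and above 120%, plus a listing. SAP 1.2 describes the treatment period: "Starts with the first dose of study drug (Day 1 of study) and ends with EOT".

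Protocol 6.5 is also per strength, but its denominator is the "total number of tablets that should have been taken during the period". A footnote to that formula names the source: "According to the study intervention administration log". Site personnel calculate this value at each site visit and enter it in the eCRF. Values outside 80–120% between visits are reported as protocol deviations.

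Protocol Table 2 gives one week to each level from 200 to 1400 µg and reaches 1600 µg on Day 50. For Weeks 9–12 it allows a "Buffer period to permit up/down-titration to ensure IMD is reached at the end of Week 12". Protocol 6.2 and 6.7 provide for once-daily dosing in some participants.

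SAP 6.2, which lists changes from the protocol-planned analyses, does not mention compliance.

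**The concern.** The numerator counts tablets of one strength. The denominator counts every day of treatment at two tablets a day, whatever strength was in use. A titrating participant passes through up to eight strengths, each used for part of the period, so no single strength can be expected to fill that denominator. Strengths taken exactly as planned would be shown as below 80%, using the same cut-offs that Protocol 6.5 gives as the expected range. The study report could then contradict the values that sites recorded under the protocol formula.

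SAP 6.7 also does not say whether its three categories classify strengths or participants, so two programmers could build different tables from the same data.

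**Working it through.** The documents give no worked compliance value, so there is no stated figure to reproduce.

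**Inputs**
- One dose on Day 1, twice daily afterwards (Protocol 6.2, 6.2.1).
- One tablet per dose. This is an assumption; Protocol 6.1 lists a tablet for every dose level.
- Table 2 pace: 200 µg on Days 1–7, one new strength per week, 1600 µg from Day 50.
- Full adherence and all unused tablets returned (assumption).
- Treatment duration T of 28, 84, 182 or 364 days. These are illustrations; the documents do not give actual durations. Table 2 ends at Day 364.

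**Formulas**
- SAP 6.7: 100 × tablets of the strength / (2 × T), taking 2 × T as the intended denominator.
- Protocol 6.5: 100 × tablets of the strength / tablets of that strength due.

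**Tablets taken**
- 200 µg: 1 + 6 × 2 = 13.
- Each later one-week strength: 7 × 2 = 14.
- 1600 µg: 2 × (T − 49), which is 70 at 84 days, 266 at 182 and 630 at 364.

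**SAP score**

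| T (days) | 2T | 200 µg | Other one-week strength | 1600 µg |
|---|---|---|---|---|
| 28 | 56 | 13/56 = 23.2% | 14/56 = 25.0% | not reached |
| 84 | 168 | 13/168 = 7.7% | 14/168 = 8.3% | 70/168 = 41.7% |
| 182 | 364 | 13/364 = 3.6% | 14/364 = 3.8% | 266/364 = 73.1% |
| 364 | 728 | 13/728 = 1.8% | 14/728 = 1.9% | 630/728 = 86.5% |

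Protocol 6.5 gives 13/13, 14/14 or 630/630 = 100% in every case.

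**Strengths below 80%:** 4 of 4 at 28 days, 8 of 8 at 84 and 182 days, 7 of 8 at 364 days.

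**When the shortfall starts.** The 200 µg strength, stopped after Day 7, scores 13/16 = 81.2% if treatment lasts 8 days and 13/18 = 72.2% if it lasts 9. In general, a twice-daily strength used for less than about 80% of treatment days falls below 80%.

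**Delayed titration.** A maintenance strength first used on Day 78, inside the Table 2 buffer, scores (364 − 78 + 1)/364 = 287/364 = 78.8% at 364 days.

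**What the denominator does fit.** Summed over strengths at 364 days, 13 + 6 × 14 + 630 = 727 and 727/728 = 99.9%. A participant who stays on 200 µg throughout is likewise unaffected: 55/56 = 98.2% at 28 days, 727/728 = 99.9% at 364.

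**Alternative reading: duration means time on that strength.** Twice daily, a one-week strength scores 14/14 = 100%, or 13/14 = 92.9% for the first week. Once daily, it scores 7/14 = 50%.

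**Once daily with the whole period as denominator.** Starting on Day 2 and summing over strengths, 363/728 = 49.9% at 364 days.

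**Sensitivity.** Counting each switch from the evening dose moves one tablet between neighbouring strengths: 1/728 = 0.14 points at 364 days, 1/56 = 1.8 points at 28 days. No conclusion changes.

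**The case against.** The strongest reply is that the formula is introduced as per strength, so its treatment period may mean the time on that strength, parallel to Protocol 6.5. SAP 6.7 does not refer back to SAP 1.2. On that reading the twice-daily scores above become 92.9–100%. This is possible but weaker: the formula refers to a total duration, the summary runs through EOT, and SAP 1.2 describes the period as first dose to EOT. The fixed factor 2 would still halve the score for once-daily dosing, so the text needs an edit either way.

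The second reply stands. Sites already calculate compliance with the protocol formula and enter it in the eCRF, and deviations are reported from that route. A reader might infer that SAP 6.7 would generate false protocol deviations or remove participants from an analysis set. The documents do not support this: SAP 6.7 does not feed deviation reporting, and SAP 4 keeps only the screened and safety sets.

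A reader might also infer inflated scores from Protocol 4.3, which allows several tablets per dose. Since Protocol 6.1 lists a tablet for each dose level, that case is marginal. Nor should weight be put on the missing bracket around the denominator: the intent is clear, and a fraction flattened in text extraction would look the same.

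Finally, after early termination the actual durations are unknown, so the 364-day figures illustrate the formula and do not predict the report.

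**Conclusion.** The point holds as a minor one. On its more natural reading, SAP 6.7 replaces the protocol denominator, without saying so, by one that does not match a per-strength numerator. The percentages assume full adherence, one tablet twice daily, the Table 2 pace and full return of unused tablets; the mismatch itself does not depend on those assumptions. Even on the more generous reading, once-daily participants score about 50%. The consequence is limited to one descriptive table and one listing. Efficacy is reported by listings only, and exposure and dose are summarised separately under SAP 5.6.1.

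**What to change.** In SAP 6.7, use the Protocol 6.5 formula per strength: 100 × (tablets dispensed − tablets returned) / (tablets of that strength due according to the administration log). Alternatively, report the site-calculated values already in the eCRF. These are per visit interval, so the SAP would need to say how they are combined through EOT.

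Add one sentence stating whether the three categories apply per strength or per participant. Summing numerator and denominator over strengths, to classify each participant once, is one option. Its drawback is that over-use of one strength can offset under-use of another. Whichever is chosen, the existing condition that accountability was performed should govern numerator and denominator alike.

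The cost is one formula and one sentence in the SAP, and reprogramming of one table and one listing. The documents do not say whether tablets due can be derived directly from the database; if they cannot, the eCRF values avoid the problem.

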6.3. Preparation/Handling/Storage/Accountability

Study intervention supplies must be kept in an appropriate, secure area and stored according to the conditions specified on the label. See the pharmacy manual/study-site investigational product and procedures manual for additional guidance on study intervention preparation, handling, and storage.

Participants will be asked to return all used, partially used, and unused study intervention bottles at each visit. The protocol-mandated study intervention dispensing procedures may not be altered without prior written approval from the sponsor. The interactive web response system will allow dispensation of study intervention outside scheduled visits. An accurate record of the date, strength, and amount of study intervention dispensed to each participant must be available for inspection at any time.

The investigator is responsible for ensuring that all study intervention received at the site is inventoried and accounted for throughout the study. The dispensing of study intervention (strength

and number of dispensed bottles and date dispensed/strength and number of tablets dispensed) to the participant, and the return of study intervention (date returned/strength and number of tablets returned) from the participant (if applicable), must be documented on the intervention accountability form. Participants must be instructed to return all original containers, whether empty or containing study intervention. All study intervention will be stored and disposed of according to the sponsor's instructions. Study-site personnel must not combine contents of the study intervention containers. If the participant forgets to bring the remaining study intervention to a study visit, participant must be instructed to not take any tablets from the remaining study intervention bottle and to return it at the next visit.

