### **5.1.5. Up-titration period end date**

It is the date of Week 12 visit from the "Medication Kit Dispensation/ Accountability [IWRs or Balance]" eCRF form. In case of premature discontinuation or death prior to Week 12, the 'End of Treatment Date' in the "End of Treatment" eCRF form or the date of death will be considered. If both dates are missing and the subject discontinued from the study prior to Week 12, the 'End of Trial Date' from the "End of Trial" form will be used.

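### SAP 6.7 divides by the whole treatment period but does not say at what level its drug-accountability condition applies, so partial accountability can misclassify a participant or leave no compliance value

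*SAP*

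**What the plan says.** SAP Appendix 7 (Section 6.7) sets the unit of calculation: "Compliance will be calculated as follows, for each strength dispensed". The ratio is "number of tablets dispensed - number of tablets returned)/2 x total duration of treatment period", evidently meant as tablets used over two tablets a day for the whole treatment period. The accountability condition follows: "Compliance will be calculated only if the answer to the question" about returned study treatment is 'Yes'. Results are summarised through end of treatment in three bands, "< 80%, 80–120% and > 120" percent. The appendix ends with "Compliance will also be listed". It gives no row for participants without a value, no rule for partial accountability and no analysis set for the percentages, although Appendices 5 and 6 next to it name the Safety Set.

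Protocol 6.5 works differently. Site staff calculate compliance at each site visit, dividing tablets used by the tablets due in that same interval according to the administration log. The limits belong to that interval: "Between visits, compliance is expected to be between 80% and 120" percent. SAP Appendix 2, which records changes to planned analyses, does not mention the new denominator.

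Two further places bear on how accountability is collected. SAP 5.1.5 refers to an eCRF form called "Medication Kit Dispensation/ Accountability [IWRs or Balance". Protocol 6.3 covers the case "If the participant forgets to bring the remaining study intervention to a study visit": the bottle is not to be used further and is to be returned at the next visit.

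**The concern.** A compliance ratio makes sense only if its two parts cover the same days. The protocol's formula ensures this and the SAP's does not. Its denominator is always the full treatment period, while the condition on accountability can limit which dispensings contribute tablets.

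Because the level of the condition is not stated, the same fully adherent participant with one unaccounted dispensing could be programmed in at least three ways:

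- **Per kit or visit:** the tablets of that dispensing drop out, its days stay in the denominator, and the ratio falls.
- **Any 'No' blocks the calculation:** the participant has no value and belongs to none of the three bands.
- **Any 'Yes' is enough:** unreturned tablets are counted as taken.

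At stake is whether the compliance table can be read at all where returns are incomplete. With the very limited number of participants that SAP 5.3.2 describes, one misplaced participant would show.

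**Working it through.** The documents give no compliance figure to reproduce, so the check applies the SAP formula to a fully adherent participant.

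**Inputs**
- Two doses a day (Protocol 6.1); one tablet per dose is assumed.
- Return or dispensing visits at the ends of Weeks 4, 12, 26, 39 and 52 (Protocol 4.1 and Table 1), nominally Days 28, 84, 182, 273 and 364.
- Each dispensing covers the period to the next scheduled visit (Protocol 6.3).
- Strengths pooled into one value. This is an assumption, because the SAP gives no pooling rule.

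**Full accountability.** With one dose on Day 1, 727/728 = 99.9%. Below, two tablets are counted on every day; the single Day 1 dose changes a result by at most 1/728 = 0.14 percentage points.

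**Per-kit or per-visit condition, one dispensing interval unaccounted for.** Compliance = (364 − L)/364, where L is the length of that interval in days.

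| Interval | L | Result |
|---|---|---|
| Day 1 to Week 4 | 28 | 336/364 = 92.3% |
| Weeks 4-12 | 56 | 308/364 = 84.6% |
| Weeks 12-26 | 98 | 266/364 = 73.1% |
| Weeks 26-39 | 91 | 273/364 = 75.0% |
| Weeks 39-52 | 91 | 273/364 = 75.0% |

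The target days 84, 180, 270 and 360 give 264/360 = 73.3% and 270/360 = 75.0% (twice) for the maintenance intervals.

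**Visit windows** (Week 12 on Days 84-91, Week 26 on Days 168-196, Week 39 at ±14 days as in Table 1, end of treatment on Days 350-378)
- Weeks 12-26: from 238/350 = 68.0% to 301/378 = 79.6%.
- Weeks 26-39: from 231/350 = 66.0% to 315/378 = 83.3%.
- Weeks 39-52: from 259/378 = 68.5% to 287/350 = 82.0%.

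**Size of gap needed.** To fall below 80% of 364 days, more than 0.20 × 364 = 72.8 days must be unaccounted for, or more than 145.6 tablets. One missing 60-tablet bottle (an illustrative size, since the documents give none) leaves 668/728 = 91.8%.

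**Shorter treatment.** With treatment ending on Day 182 and the Week 12 dispensing unaccounted for, the result is 84/182 = 46.2%.

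**Any 'No' blocks the calculation.** No value exists, so there is nothing to band.

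**Period-matched calculation.** With the Week 12-26 interval left out of both parts, the same completer scores 531/532 = 99.8% if two tablets are expected on Day 1, and 100% if the log expects one.

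**The case against.** The strongest reply is that SAP 6.7 places a condition on the calculation of compliance, not on the tablet count. Nowhere does it say that tablets from unaccounted kits are dropped while the rest are summed over the full period. The form name in SAP 5.1.5 makes a kit-level answer plausible but does not establish it. This stands, so the 73-75% result is conditional.

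A reader might infer from Protocol 6.3 that forgotten bottles will be lost to the count. The text supports less: such a bottle is due back at the next visit, and a summary through end of treatment could still include it. The documents do not say how often bottles are never returned.

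The figures also need a whole 13-14 week dispensing to be missing and strengths to be pooled. Read literally per strength, a strength first taken on Day 85 scores 280/364 = 76.9% even with every tablet accounted for. That is a separate fault in the same formula. Correcting it alone, by taking expected tablets over the whole period, would leave the mismatch described here.

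Finally, the consequences are small. Efficacy is listings only, no per-protocol set is kept, and no planned analysis uses the compliance bands. Individual compliance is listed, SAP 5.6.1 summarises doses not administered with reasons, and sites enter the period-matched values in the eCRF. All of this stands and limits the weight of the point, but it does not supply the missing rule.

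**Conclusion.** The point holds in a conditional form and is minor. It is explicit that the denominator is the full treatment period, that a value depends on a 'Yes', that only three bands exist, and that the protocol's matched formula has been replaced without an entry in Appendix 2. The level at which the condition works is not stated.

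Under a kit- or visit-level reading, a natural one for a question about returned drug, one whole unaccounted maintenance interval puts a fully adherent completer at about 73-75%. This assumes nominal visit days, pooled strengths and one tablet per dose. Under a blocking reading the participant has no value and no category.

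Three stronger inferences are not supported. The SAP does not definitely place adherent participants below 80%. Nothing shows that participants without a value are the least adherent, or that the table will therefore flatter compliance. Nothing links the bands to how the RVSV change is analysed. The effect stops at the descriptive compliance table and the reading of exposure.

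**What to change.** In SAP 6.7, define compliance as tablets used divided by tablets expected per the administration log, both taken over the same between-visit periods and only those with accountability performed, as in Protocol 6.5. Report the share of each participant's treatment days that these periods cover. Add a row for participants not evaluable because accountability was not performed, with all percentages out of the Safety Set.

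This takes about two sentences and one table row, and no new data. The small downside is that compliance rests on fewer days for participants with unaccounted kits; the coverage figure makes that visible.
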